9.5.6 Abuse or Diversion of Study Drug

During the study, the investigator will report any concern about abuse or diversion of study drugs by completing the Abuse or Diversion of Study Drug CRF. The DEA Registrant has the responsibility to comply with local, state, and Federal laws to notify the Field Division Office of the DEA of any theft or significant loss of any controlled substances upon discovery of such theft or loss.

9.5.7 Confirmation of Medical Care by Another Physician

The investigator will instruct subjects to inform site personnel when they are planning to receive medical care by another physician. At each visit, the investigator will ask the subject whether he or she has received medical care by another physician since the last visit or is planning to do so in the future. When the subject is going to receive medical care by another physician, the investigator, with the consent of the subject, will inform the other physician that the subject is participating in the clinical study.

9.6 Data Quality Assurance

This study will be organized, performed, and reported in compliance with the protocol, SOPs, working practice documents, and applicable regulations and guidelines. Site audits will be made periodically by the sponsor’s or the CRO’s qualified compliance auditing team, which is an independent function from the study team responsible for conduct of the study.

9.6.1 Data Collection

Data required by the protocol will be collected on the CRFs and entered into a validated data management system that is compliant with all regulatory requirements. As defined by ICH guidelines, the CRF is a printed, optical, or electronic document designed to record all of the protocol-required information to be reported to the sponsor on each study subject.

Data collection on the CRF must follow the instructions described in the CRF Completion Guidelines. The investigator has ultimate responsibility for the collection and reporting of all clinical data entered on the CRF. The investigator or designee as identified on Form FDA 1572 must sign the completed CRF to attest to its accuracy, authenticity, and completeness.

Completed, original CRFs are the sole property of Eisai and should not be made available in any form to third parties without written permission from Eisai, except for authorized representatives of Eisai or appropriate regulatory authorities.

9.6.2 Clinical Data Management

All software applications used in the collection of data will be properly validated following standard computer system validation that is compliant with all regulatory requirements. All data, both CRF and external data (eg, laboratory data), will be entered into a clinical system.

9.7 Statistical Methods

All statistical analyses will be performed by the sponsor or designee after the study is completed and the database is locked and released for unblinding. Statistical analyses will be performed using WinNonlin and SAS software or other validated statistical software as required. Details of the statistical analyses will be included in a separate statistical analysis plan (SAP).

9.7.1 Statistical and Analytical Plans

The statistical analyses of study data are described in this section. Further details of the analytical plan will be provided in the SAP, which will be finalized before database lock and treatment unblinding.

9.7.1.1 Study Endpoints

9.7.1.1.1 PRIMARY EFFICACY ENDPOINT

- Change in BMI from baseline to Week 52

9.7.1.1.2 SECONDARY EFFICACY ENDPOINTS

KEY SECONDARY ENDPOINT

- Proportion (%) of subjects achieving at least a 5% BMI reduction at Week 52

OTHER SECONDARY ENDPOINT

- Proportion (%) of subjects achieving at least a 5% BMI reduction at Week 12
- Proportion (%) of subjects achieving at least a 10% BMI reduction at Week 52
- Percentage change in BMI from baseline to Week 52
- Association between change and percentage change in BMI from baseline to Week 52 with the outcome of achieving at least a 5% BMI reduction at Week 12 (revised per Amendment 02)
- Association between the proportion (%) of subjects achieving at least a 5% or 10% BMI reduction at Week 52 with the outcome of achieving at least a 5% BMI reduction at Week 12 (revised per Amendment 02)
- Change in waist circumference from baseline to Week 52
- Change in total body composition (total fat and lean mass) in a subset of randomized subjects at end of 52 weeks of treatment (revised per Amendment 03)
- Change in HbA_{1c} from baseline to Week 52 for subjects with T2DM at baseline (revised per Amendment 03)
- Change in fasting plasma glucose, fasting insulin, and HOMA-IR from baseline to Week 52 for subjects with T2DM at baseline (revised per Amendments 03 and 04)
- Change in fasting plasma glucose, fasting insulin, and HOMA-IR from baseline to Week 52 for the subjects without T2DM at baseline (revised per Amendments 03 and 04)
- Change in BP (systolic and diastolic) and heart rate from baseline to Week 52
- Change in fasting lipid profile (total cholesterol, LDL cholesterol, HDL cholesterol, triglycerides) from baseline to Week 52
- Proportion (%) of subjects with prehypertension or primary hypertension at Week 52
- Proportion (%) of subjects with dyslipidemia at Week 52
- Subject compliance rate at each visit by pill count during 52 weeks of treatment (per Amendment 03)

9.7.1.2 Definitions of Analysis Sets

- The Safety Analysis Set is the group of subjects who received at least 1 dose of study drug and had at least 1 postdose safety assessment.

- The Full Analysis Set (FAS) is the group of all randomized subjects regardless of adherence to study drug.
- Per-Protocol Analysis Set (PP) is the group of all randomized subjects who are 80% or greater compliant with study medication, completed the study, have no major protocol deviations, have no violations of inclusion or exclusion criteria, and have BMI data at baseline and Week 52. The determination of subjects to be excluded from this population based on the above criteria and list of major protocol violations will be included in the SAP and finalized before data base lock.
- The PD Analysis Set is the group of subjects who had sufficient PD data to derive at least 1 PD parameter.
- The PK Analysis Set is the group of all randomized subjects from whom at least 1 valid lorcaserin plasma concentration was obtained with associated documented dosing history.
- The population PK/PD set is the group of randomized subjects with PK information and who have at least 1 adequately documented measurement of BMI.

9.7.1.3 Subject Disposition

The number of subjects screened and the number (percentage) of subjects who failed screening and the reasons for screen failure will be summarized, based on data reported on the CRF.

For study completion, the number (percentage) of treated subjects who completed study treatment and who discontinued from study treatment will be summarized according to the primary reason for discontinuation and also according to secondary reason(s) for discontinuation, based on data reported on the CRF. The number (percentage) will be presented by treatment. The reasons for discontinuation from study treatment will be documented in the CRF and source documentation.

9.7.1.4 Demographic and Other Baseline Characteristics

Demographic and other baseline characteristics for the FAS and Safety Analysis Sets will be summarized for each treatment group using descriptive statistics or frequency count. Continuous demographic and baseline variables include age, height, BMI, waist circumference, and weight; categorical variables include sex and race.

9.7.1.5 Prior and Concomitant Therapy

All investigator terms for medications recorded in the CRF will be coded to an 11-digit character code using the World Health Organization Drug Dictionary. The number (percentage) of subjects who took prior and concomitant medications will be summarized for the Safety Analysis Set by treatment group, Anatomical Therapeutic Chemical class, and World Health Organization Drug Dictionary preferred term (PT). Prior medications will be defined as medications that stopped before the first dose of study drug. Concomitant

medications will be defined as medications that started on or after the date of the dosing of study drug and continued up to 30 days afterward.

9.7.1.6 Efficacy Analyses

The FAS will be used as the primary analysis set for all efficacy analyses, while the PP will be used as a supportive analysis. Unless specified otherwise, a 2-sided $\alpha=0.05$ significance level will be used for all efficacy analyses.

Primary Efficacy Analysis

The primary efficacy endpoint is the change in BMI from baseline to Week 52. The change from baseline in BMI will be analyzed using analysis of covariance model (ANCOVA) with factors of treatment, sex (male and female) as fixed effect, and the baseline age and BMI as covariates. The missing values will be imputed using a pattern mixture model utilizing multiple imputation (MI) assuming the missing values are missing not at random (MNAR). The missing values will be imputed at each visit using all available values including the retrieved measurement from the postdiscontinuation data. The details of the analysis model and missing value imputation method will be further described in the SAP.

In addition, the following analyses will also be considered as sensitivity analyses:

- PP analysis: The same primary efficacy analyses described above will be repeated based on the PP.
- Change from baseline in standardized BMI score (Z-score): The same primary efficacy analyses described above will be repeated using Z-score.

Subgroup analyses and additional sensitivity analyses, if appropriate, may also be performed and will be described in the SAP.

Key Secondary Efficacy Analysis

The key secondary efficacy endpoint is the proportion of subjects achieving at least a 5% BMI reduction at Week 52. The secondary efficacy endpoint will be analyzed only if the test for the primary efficacy endpoint is statistically significant.

The proportion of subjects achieving at least a 5% BMI reduction at Week 52 will be analyzed using a logistic regression model with factors of treatment, and sex (male and female), and baseline BMI as a covariate using FAS. Subjects with any missing assessment at Week 52 will be considered as treatment failures in this analysis.

Other Secondary Efficacy Analyses

Unless specified, for all other secondary efficacy endpoints, the continuous variables will be analyzed using mixed effect model repeated measurement analysis (MMRM) on the FAS for study treatment compared to placebo, as appropriate. The model will include all data and will include treatment, time, and the interaction of treatment by time as fixed effects, with adjustment for sex (male versus female), BMI and age at baseline, and subject as a random effect. (revised per Amendment 03)

Treatment by time interaction will be used to construct the treatment comparisons at a specific time. The MMRM model assumes that the missing data are missing at random and makes use of all available data even if a subject has missing data at some postbaseline visits. An unstructured covariance matrix will be used, and if the model fails to converge, then an autoregressive matrix will be used. (revised per Amendment 03)

Categorical variables will be analyzed using the Cochran Mantel Haenszel test, Chi-square test, or logistic regression as appropriate. Additional analysis may be performed as needed using appropriate statistical methodologies as specified in SAP.

Subgroup analyses will be performed on the primary efficacy endpoint, including sex (male and female), race (American Indian or Alaska Native, Asian, Black or African American, Native Hawaiian or other Pacific Islander, or White), and age. Additional subgroups may be explored, if deemed necessary. (revised per Amendment 03)

No adjustment for multiplicity is planned for other secondary endpoints, subgroup, and sensitivity analyses.

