The key secondary efficacy endpoint is the proportion of subjects achieving at least a 5% BMI reduction at

Week 52. The secondary efficacy endpoint will be analyzed only if the test for the primary efficacy endpoint is statistically significant.

The proportion of subjects achieving at least a 5% BMI reduction at Week 52 will be analyzed using a logistic regression model with factors of treatment, sex (male and female), and baseline BMI as a covariate using FAS. Subjects with any missing assessment at Week 52 will be considered as treatment failures in this analysis.

Other Secondary Efficacy Analyses

Unless specified, for all other secondary efficacy endpoints, the continuous variables will be analyzed using mixed effect model repeated measurement analysis (MMRM) and categorical variables will be analyzed using the Cochran Mantel Haenszel test, Chi-square test, or logistic regression as appropriate. Additional analysis may be performed as needed using appropriate statistical methodologies as specified in SAP.

Subgroup analyses will be performed on the primary efficacy endpoint, including sex (male and female), and race (American Indian or Alaska Native, Asian, Black or African American, Native Hawaiian or other Pacific Islander, or White) and age. Additional subgroups may be explored, if deemed necessary.

No adjustment for multiplicity is planned for other secondary endpoints, subgroup, and sensitivity analyses.

Pharmacokinetic Analyses

Lorcaserin plasma concentration-time data will be subjected to population PK analysis using nonlinear mixed effects modeling. The effect of covariates such as baseline characteristics or demographics on PK will be explored. Derived exposure parameters such as the maximum observed concentration and the area under the concentration-time curve from time 0 to 24 hours at steady-state will be calculated from the final PK model using individual posterior estimates of the PK parameters and from dosing history. The PK analysis set will be used for this analysis.

Pharmacodynamic Analyses

Change from baseline in BMI will be assessed as the PD endpoint. The PD analysis set will be used for this analysis.

Other assessments (eg, percentage of BMI change, proportion [%] of subjects achieving $\geq 5\%$ and $\geq 10\%$ BMI reduction, and change in waist circumference from baseline) will also be assessed as part of the PD analysis. The PK/PD analysis set will be used for this analysis.

Pharmacokinetic/Pharmacodynamic Analyses

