9.7.2 Determination of Sample Size

The proposed sample size is based on the comparison of the primary efficacy endpoint, change from baseline in BMI at Week 52 between the Belviq XR 20-mg treatment group and placebo group. Assuming a SD of 2.2 kg/m² and a 40% dropout rate, a sample size of 260 subjects in a 1:1 ratio (n=130 in the Belviq XR 20-mg treatment group; n=130 in the placebo group) will have at least 80% power to detect a treatment difference of 1 kg/m² in BMI, using a 2-sided t-test with $\alpha=0.05$. Assuming the proportion of subjects achieving at least a 5% BMI reduction at Week 52 is 20% for the placebo group and a 40% dropout rate, this sample of 260 subjects (130 subjects for Belviq XR 20 mg and 130 subjects for placebo) will also have greater than 78% power to detect an absolute difference of 20% between the Belviq XR 20-mg group and placebo group, using a 2-sided Chi-Square test with $\alpha=0.05$. The assumption used in the sample size calculation is based on the 2 pivotal lorcaserin studies, APD356-009 and APD356-011 in obese and overweight non-diabetic adult subjects. (revised per Amendment 02)

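### The key secondary responder model leaves out baseline age, which the primary ANCOVA adjusts for; adding it is a near-free improvement

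*Protocol*

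**What the plan says.** Section 9.7.1.6 specifies the key secondary analysis as a "logistic regression model with factors of treatment, and sex (male and female), and baseline BMI as a covariate using FAS", with subjects missing the Week 52 assessment counted as failures. The synopsis gives the same list: "logistic regression model with factors of treatment, sex (male and female), and baseline BMI as a covariate using FAS". The omission is therefore consistent across the protocol and does not look like a slip in one place.

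The primary ANCOVA in the same section is fitted "with factors of treatment, sex (male and female) as fixed effect, and the baseline age and BMI as covariates". The MMRM for the other continuous secondary endpoints is fitted "with adjustment for sex (male versus female), BMI and age at baseline, and subject as a random effect".

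Section 9.4.3 stratifies randomization by sex and by nothing else. Section 9.1 sets a recruitment floor of 20% for subjects aged 12 to 13 within a 12 to 17 year range. Age is collected as demography at the first visit (Section 9.5.1.1). The protocol fixes the responder model's covariates itself and does not leave them to the SAP.

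**The concern.** The responder endpoint is a cut of the variable that the primary analyses, and it is the only test gated behind the primary. The protocol judged age worth adjusting for in the continuous models and names it as a subgroup factor, but drops it here without explanation. Eligibility rests on an age- and sex-specific BMI percentile, and a BMI Z-score sensitivity analysis is planned, so the protocol treats expected BMI as depending on age.

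Two modest things are at stake. If age predicts response, a model without it gives up some attainable precision. And because age is not a stratification factor, its balance rests on chance: the primary corrects an imbalance, while the responder model does not.

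**Working it through.** **Stated power.** Section 9.7.2 begins "Assuming the proportion of subjects achieving at least a 5% BMI reduction at Week 52 is 20% for the placebo group and a 40% dropout" and concludes that the trial "will also have greater than 78% power to detect an absolute difference of 20% between the Belviq XR 20-mg group and placebo group", by a two-sided chi-square test at 0.05. Inputs: 130 × (1 − 0.40) = 78 per arm, 20% versus 40%, mean proportion 0.30.

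- Null SE = √(2 × 0.30 × 0.70 / 78) = 0.0734
- Alternative SE = √((0.20 × 0.80 + 0.40 × 0.60) / 78) = 0.0716
- Power = Φ((0.20 − 1.96 × 0.0734) / 0.0716) = 78.4%

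The stated figure reproduces with no covariate at all.

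**Scenario matching the planned analysis.** The analysis keeps all 130 per arm and counts missing as failure. If 40% are missing equally in both arms and the 20% and 40% rates apply to those assessed, the rates become 0.60 × 20% = 12% and 0.60 × 40% = 24%. The same formula gives 71.4%. Expected responders: 130 × 0.12 + 130 × 0.24 ≈ 47, enough to carry one more covariate.

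**Effect of adding age.** Simulation of the two-sided Wald test for treatment in the logistic model, with 4,000 trials per row and both models fitted to the same data. Age is taken as uniform over 12 to 17 years (SD about 1.7 years). Sex and baseline BMI are given log-odds of 0.2 each (assumed). Intercepts are re-solved in each row so that the marginal response rates stay fixed. The protocol gives no association between age and response, so the odds ratio per SD of age is an assumption, varied from 1.0 to 3.0. Monte Carlo error is about 0.6 to 0.7 points per power figure.

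| OR per SD of age | 130 per arm, 12% vs 24%: without → with age | 78 per arm, 20% vs 40%: without → with age |
|---|---|---|
| 1.0 | 72.3% → 72.3% | 79.1% → 79.0% |
| 1.25 | 71.5% → 72.0% | 78.6% → 78.8% |
| 1.5 | 70.6% → 71.8% | 79.0% → 79.8% |
| 2.0 | 71.2% → 73.4% | 79.6% → 82.8% |
| 3.0 | 71.2% → 77.1% | 78.6% → 85.5% |

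With no treatment effect (78 per arm, 20% in both arms, odds ratio 1.5), the rejection rate is about 4.7% with or without age.

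**Chance imbalance.** At 130 per arm the mean age difference has standard error √(2/130) = 0.124 SD, so a 1.96-SE imbalance is about 0.24 SD. At an assumed odds ratio of 1.5 to 2.0 per SD, this shifts the treatment log-odds by about 0.24 × ln 1.5 = 0.10 to 0.24 × ln 2.0 = 0.17. The log-odds difference between 24% and 12% is ln(0.24/0.76) − ln(0.12/0.88) = 0.84, so the shift is roughly 12% to 20% of the effect.

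**The case against.** The strongest reply is that nothing is wrong with the model. It is prespecified, it contains the one stratification factor, and its type I error is correct. All of that stands. The comparison is also narrower than it first looks: both analyses that include age are for continuous outcomes, and for the other categorical endpoints the protocol names no age adjustment. The ANCOVA is the closer comparator because it uses the same Week 52 BMI.

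Three stronger readings are tempting, and the protocol supports none of them:

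- A reader might infer that planned power is lost. It is not. The figure in Section 9.7.2 comes from an unadjusted test, so age adjustment was never counted on; what is forgone is an optional gain. That does not justify leaving age out, since the same figure takes no credit for sex or baseline BMI either, and both are in the model.
- A reader might infer that the primary and key secondary tests would disagree because of age. The responder test is run only after the primary succeeds, and the two already differ in dichotomisation and in missing-data handling (multiple imputation under MNAR versus missing as failure). With 40% dropout assumed, those are more obvious sources of divergence than a chance age imbalance.
- A reader might take the remark on growth in Section 7.1.2 as evidence that age predicts response. It says that BMI was chosen to allow for growth. It does not show that age predicts a 5% reduction, and no figure in the protocol does.

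**Conclusion.** This is an unexplained inconsistency in the covariate sets, of low severity, with a near-costless remedy. It does not threaten the validity of the key secondary test or its stated power.

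In the missing-as-failure scenario, the gain from adding age is about 0 to 1 point of power for an odds ratio of 1.0 to 1.5 per SD of age, about 2 points at 2.0 and about 6 points at 3.0, with no loss beyond simulation error if age is unrelated to response. Protection against a chance age imbalance comes with it. The size rests wholly on the assumed age effect, and on the assumptions of equal missingness in the two arms and of planning rates that apply to assessed subjects. The case for the change does not depend on a large gain: a covariate already judged relevant for the primary can be added at almost no cost.

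**What to change.** Before unblinding, amend the key secondary model in Section 9.7.1.6 and in the synopsis to treatment, sex, baseline age and baseline BMI, the same covariate set as the primary ANCOVA, and carry the same list into the SAP. If the sponsor prefers to leave age out, the reason should be stated.

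The cost is a few words. Age is already collected, and no sample-size change is needed. The one small downside is interpretive: the treatment odds ratio is then conditional on age as well as on sex and baseline BMI.

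### The key secondary counts a missing Week 52 BMI as failure while the primary imputes it; the test then depends on retention, and the stated power of over 78% does not follow from that rule (about 72% at 40% missing)

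*Protocol*

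**What the plan says.** Protocol 9.7.1.1.2 lists the key secondary endpoint as "Proportion (%) of subjects achieving at least a 5% BMI reduction at Week 52". Section 9.7.1.6 analyses it by logistic regression with treatment, sex and baseline BMI on the Full Analysis Set, which 9.7.1.2 defines as all randomized subjects. It adds that "Subjects with any missing assessment at Week 52 will be considered as treatment failures in this analysis". The Synopsis repeats the rule. The test is gated: "The secondary efficacy endpoint will be analyzed only if the test for the primary efficacy endpoint is statistically significant".

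For the primary endpoint, change in the same Week 52 BMI, 9.7.1.6 instead prescribes pattern-mixture multiple imputation under a missing-not-at-random assumption, "using all available values including the retrieved measurement from the postdiscontinuation data". Details of that imputation are left to the SAP. The failure rule is not.

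Section 9.7.2 and the Synopsis give the key secondary more than 78% power for a 20-point difference with 130 per arm and a two-sided chi-square test at 0.05, assuming "20% for the placebo group and a 40% dropout rate". Section 9.5.1.3 sets a best-effort target of at least 80% of randomized subjects with a primary endpoint assessment, on drug or not.

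**The concern.** The objective and the endpoint concern the proportion who reduce BMI by 5% or more. Neither makes attendance at Week 52 part of response. Scoring a missing value as failure does exactly that, because an arm's observed rate becomes its true response rate times its retention. If retention differs, the two arms can have equal response and unequal observed rates, or the reverse.

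The rule is not a strategy for treatment discontinuation either. Subjects who stop drug are followed and, if weighed at Week 52, are scored on their actual BMI. A subject still on drug who misses the visit is a failure.

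Separately, the power statement seems to treat dropouts as lost sample size, whereas the analysis rule keeps them in the denominator as failures. The key secondary is the only formally gated claim after the primary, so both its meaning and its power matter.

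**Working it through.** **Inputs from the protocol.** 130 per arm; two-sided alpha 0.05, chi-square; true response 20% placebo and 40% active (20% plus the 20-point difference); 40% dropout overall (9.7.2); target of at most 20% missing (9.5.1.3). **Assumptions made here.** Missingness is unrelated to response. Every split of missingness between arms is assumed, since the protocol gives one overall rate. Covariates are ignored, as in the protocol's own calculation.

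**Step 1: reproduce the stated power.** Completers per arm = 130 × (1 − 0.40) = 78. With mean rate 0.30, the pooled standard error is √(2 × 0.30 × 0.70 / 78) = 0.0734. The standard error under the alternative is √((0.20 × 0.80 + 0.40 × 0.60) / 78) = 0.0716. Power = Φ((0.20 − 1.96 × 0.0734) / 0.0716) = Φ(0.784) = 78.4%. Exact binomial enumeration of the chi-square test gives 78.9%. The stated figure is reproduced with dropouts removed.

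**Step 2: apply the written rule at 40% missing in each arm.** Observed rate = true rate × (1 − missing):
- placebo 0.20 × 0.60 = 0.12
- active 0.40 × 0.60 = 0.24

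The denominator is 130 per arm. The standard errors are √(2 × 0.18 × 0.82 / 130) = 0.0477 and √((0.12 × 0.88 + 0.24 × 0.76) / 130) = 0.0471. Power = Φ((0.12 − 1.96 × 0.0477) / 0.0471) = Φ(0.565) = 71.4%, or 71.9% by exact enumeration. About 160 per arm would be needed for 80%. No retention imbalance is assumed here.

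**Step 3: the same if the 80% target is met.** The rates are 0.20 × 0.80 = 0.16 and 0.40 × 0.80 = 0.32, giving power 86.0% (exact 86.4%). Removing dropouts (104 per arm, 20% vs 40%) would give about 89%, so the rule costs less when fewer values are missing.

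**Step 4: unequal missingness (exact enumeration, 130 per arm, before the gate is applied).**

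| True response | Missing | Observed rates | Result |
|---|---|---|---|
| 30% both arms | 40% / 40% | 18.0% / 18.0% | rejects 4.9% |
| 30% both arms | 35% / 45% | 19.5% / 16.5% | rejects 9.5% |
| 30% both arms | 15% / 25% | 25.5% / 22.5% | rejects 8.7% |
| 40% active, 20% placebo | 45% active, 35% placebo | 22% / 13% | power 48% |
| 40% active, 20% placebo | 25% active, 15% placebo | 30% / 17% | power 70% |

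In the two unequal equal-response rows, nearly all rejections favour the better-retained arm (9.05 of the 9.5 percentage points in the first, 8.1 of the 8.7 in the second).

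**The case against.** Missing-as-failure is a familiar, unambiguous convention for responder endpoints, and different missing-data rules for a mean and a proportion are not in themselves an error. With equal retention, type I error stays at about 5%. These points stand, but they do not repair the power statement.

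The gate also stands as a limit. With no effect on either endpoint, a false key secondary claim cannot occur more often than the primary's 5%. The false-positive risk is therefore confined to the case where mean BMI truly differs but 5% response does not. The gate does nothing for the power loss.

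The protocol separates stopping drug from missing the assessment: it follows discontinuers, allows home visits, and targets 80% assessed. That target was added by Amendment 03, after Amendment 02 had revised the sample size text. It could well keep missingness below 40%, but it is a goal, and 9.7.2 still plans on 40%.

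Three stronger readings are tempting and are not supported:
- A reader might infer false rejection of 24% to 33%, or power of only 25%. Those figures need a 20-point retention gap at 40% average missing and ignore the gate. Nothing in the protocol points to such a gap.
- A reader might infer that no planned analysis would expose the problem. Section 9.7.1.6 makes the Per-Protocol set supportive for all efficacy analyses, and 9.7.1.2 requires its members to have Week 52 BMI, so a Per-Protocol responder analysis contains no subject failed for missingness. It is a selected set, so it answers the point only in part.
- A reader might infer that an imputation-based analysis secures 87% to 88% power. That came from a simulation assuming a 0.7 correlation with an earlier visit and dropout unrelated to outcome. The plan's imputation is missing-not-at-random, and power under it may be lower.

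**Conclusion.** The concern holds in this form. As fixed in the protocol, the key secondary tests assessed-and-responded and matches its stated endpoint only under equal Week 52 retention. The firmest finding is the power: more than 78% is right for a calculation that drops missing subjects, but the written rule gives about 72% at the planned 40%, reading that 40% as missing Week 52 BMI as 9.7.2 itself does. If the 80% target is met with equal missingness, power is about 86%.

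The effect of unequal retention is real, but its size rests on assumed splits. A 10-point gap roughly doubles the ungated rejection rate under equal 30% response (to about 9%). If the active arm is retained worse, the same gap cuts power for 40% vs 20% to between 48% and 70%, depending on overall missingness. This should be changed, but it does not invalidate the trial's primary claim.

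**What to change.** In 9.7.1.6 and the Synopsis, pre-specify a responder analysis that derives the 5% indicator in each dataset from the primary's pattern-mixture imputation, fits the stated logistic model in each, and combines the results by Rubin's rules. Preferably make this the main key secondary analysis and keep missing-as-failure as a sensitivity analysis. At minimum, report the two together with Week 52 BMI availability by arm.

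Restate the key secondary power in 9.7.2 and the Synopsis to match the rule kept: about 72% at 40% missing in each arm if missing-as-failure remains the main analysis.

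The cost is wording in the protocol and SAP plus a little programming, since the primary already requires the imputed datasets. The downside is that the result then depends on the imputation model. Power under the plan's missing-not-at-random imputation should be worked out once the SAP has fixed its form.
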